9.8 Subsequent Visits

Not applicable

9.9 Sample Handling

No samples will be taken from patients.

9.10 Early Discontinuation/Withdrawal of Participants

During the course of the study a participant may choose to withdraw early at any time. This may happen for several reasons, including but not limited to:

- Response fatigue from the EMCAT app
- Inability to comply with study procedures
- Participant decision

Participants can withdraw from the study but permit data obtained up until the point of withdrawal to be retained for use in the study analysis. In this case, no further data would be collected after withdrawal.

Participants can also withdraw completely from the study and withdraw the data collected up until that point. The exception to this is for participants of Stream 3, who will not be able to withdraw qualitative data from semi-structured interviews once the thematic analysis has begun. In that case, the data already collected would not be used in the final study analysis. Patients will be identifiable through a study number that they are assigned at recruitment.

Once thematic analysis has begun, participants will not be able to withdraw interview data – this will be made clear in written participant information. Quantitative data, such as questionnaire responses collected by EMCAT, may be withdrawn at any time prior to the publication of analysis.

In addition, the Investigator may discontinue a participant from the study at any time if the Investigator considers it necessary for any reason including, but not limited to:

- Ineligibility (either arising during the study or retrospectively having been overlooked at screening)
- Significant protocol deviation
- Significant non-compliance with study requirements

In this case, withdrawal from the study would exclude that participant's data from the analysis if it has not already begun.

Where a participant has withdrawn, or been withdrawn, from the study, we will aim to replace that participant during the recruitment period.

The reason for withdrawal by researcher (and by participant, if this information is volunteered) will be recorded in the study file.

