9.6.1 Description of study procedure(s)

EMCAT is a progressive web application maintained by the University of Cambridge Psychometrics Centre. Each day for the first 12 weeks, it will prompt participants to complete an assessment, either by email and/or push notification. Participants undergoing steroid injection for TBOA will receive twiceweekly notifications for a further 12 weeks. When a participant receives a notification, they can choose to engage with the EMCAT app, or dismiss the notification. Those who choose to engage will either click on a hyperlink in an email, or on a push notification button to start the assessment. The application will pose questions from the PEM questionnaire which the participant will be able to respond to by clicking response options (See Appendix A).

After each response, the application will automatically select the next most useful question to administer. This process is continued until a prespecified stopping rule is met (standard error of measurement < 0.3). We expect that participants will be asked to complete between 1 and 4 questions each time they are notified. EMCAT responses will be collected for a period of 12 weeks (24 weeks for those undergoing steroid injection for TBOA). We may vary the time of day these notifications are scheduled for throughout the study, to reduce server demands.

In addition to the PEM EMCAT, each participant will be asked to complete the full-length PEM part 2 questionnaire (11 questions) at 0, 6 and 12 weeks via the app. At 12 weeks, we will ask participants to complete the User Engagement Scale (UES, 31 questions), also via the app. It is possible that participants who have had a negative experience of the app do not return UES data through it. Therefore, participants who do not respond to the UES via the app will be contacted via email and/or telephone and offered the opportunity to complete the UES either through the app reminder, over email or over the telephone. The method of response to the UES will be recorded, if not through the EMCAT platform.

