9.12 Study sequence

- 1. Potential participants will be identified by clinical members of the research team during routine care.
- 2. The clinical team members will invite potential participants to participate on the day of their treatment.
- 3. Potential participants will be provided with a written information pack, and given time to read this and discuss it.
- 4. The investigator will take informed consent from the participant at that point, if the participant feels they have had sufficient time to consider taking part.

- 5. At the point of recruitment, a member of the research team will assist the participant in downloading the EMCAT app and enabling push notifications.
- 6. At the point of recruitment, prior to the treatment, the participant will complete the full-length (11-item) PEM part 2 via the EMCAT app, and a single EMCAT assessment.
- 7. Over the next 12 weeks, participants will complete daily PEM EMCAT questionnaires (if they choose to) when prompted by email or push notification.
- 8. In addition, at 6 and 12 weeks, participants will be asked to complete the full-length PEM part 2 via the app, separately.
- 9. At 12 weeks, participants will also be asked to complete the UES via the app. Participants who do not respond with 7 days will be contacted via email or telephone and asked if they would like to return UES responses either via email or over the telephone. The method of UES response (app/email/telephone) will be recorded, if not via the ECMAT platform.
- 10. At 12 weeks, notifications will stop for all participants except those who underwent steroid injection for TBOA these participants will continue to receive EMCAT notifications twice weekly for a further 12 weeks.
- 11. For participants undergoing steroid injection for TBOA or open CTD, at the 24-week timepoint, a clinical member of the research team will review the participant's medical record and record follow-up appointment dates and (for those who underwent open CTD) whether the follow up resulted in a change of management.
- 12. Three independent clinicians will review de-identified EMCAT trajectories and appointment dates for patients who underwent open CTD, and predict whether each participant required a change in management.
- 13. We will identify and approach 10 patients and 10 clinicians with invitations to take part in semistructured interviews – interviews will take place no later than 14 days after finishing use of the EMCAT platform.

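### Section 9.10 has no step between daily prompts and leaving the study, so participants who formally withdraw before week 12 are never offered the User Engagement Scale

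*Protocol*

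**What the plan says.** Section 9.10 gives examples of why a participant might leave, the first being "Response fatigue from the EMCAT app". It then describes two forms of withdrawal by choice. In one, data already obtained are kept, but "In this case, no further data would be collected after withdrawal". In the other, "Participants can also withdraw completely from the study and withdraw the data collected up until that point". No intermediate level is described. The section adds that, after any withdrawal, "we will aim to replace that participant during the recruitment period".

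The UES has one time point. Section 9.12 (item 9) says: "At 12 weeks, participants will also be asked to complete the UES via the app". Section 9.6.1 anticipates selective non-response: "It is possible that participants who have had a negative experience of the app do not return UES data through it". It therefore provides for non-responders to be approached by email or telephone and to complete the scale by those routes.

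Usability is secondary objective 3 (section 6), measured by UES scores, response rates, response times and interviews. Section 11.4 analyses UES scores descriptively. Section 11.6 includes everyone enrolled unless withdrawn. Section 11.10 rules out imputation and sensitivity analyses.

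**The concern.** Sections 9.6.1 and 9.10 pull against each other. The first takes trouble to recover the views of people who disliked the app. The second ends all contact with anyone whose dislike was strong enough to make them withdraw, before the only occasion on which those views are sought. Prompts run daily until week 12 (section 9.12, item 10). A participant tired of them can go on dismissing them or leave the study; the protocol describes nothing in between. Section 12.5 acknowledges that someone may unsubscribe from the emails but does not say whether that person is still enrolled.

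What is at stake is the UES summary in a study that asks whether people will tolerate a daily app. The missing scores are likely to be the poorer ones, so the error probably favours the app. Withdrawers are to be replaced where possible, and no sensitivity analysis is planned, so nothing later in the plan would correct the selection. The reason for leaving is recorded only if the participant volunteers it, so the number lost to app fatigue may not be known either.

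**Working it through.** **Who is reached, on the text**

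| Participant's behaviour before week 12 | Still enrolled? | Offered the UES? |
|---|---|---|
| Keeps responding | Yes | Yes, in the app |
| Ignores or dismisses prompts | Yes (9.6.1 and 9.12 item 7 make each assessment optional) | Yes, in the app, then by email or telephone |
| Withdraws, earlier data kept | No | No (9.10) |
| Withdraws, earlier data removed | No | No (9.10) |

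The gap is the last two rows.

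**The protocol's own figures (section 11.5)**

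Inputs: difference 0.35, SD 1, power 90%, 5% level (taken as two-sided; the protocol does not say), attrition 15%.

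- Per group: 2 × (1.960 + 1.282)² / 0.35² = 171.6, rounded up to 172. This matches.
- With attrition: 172 × 1.15 = 197.8, rounded to 198 per group, 396 in total. This matches.
- Losses the target allows for: 396 − 344 = 52, which is 13.1% of 396. Taking 15% of those enrolled gives 0.15 × 396 = 59.4. The two differ because the protocol multiplies by 1.15 rather than dividing by 0.85.

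**Number never asked**

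Let s be the share of attrition that is formal withdrawal before week 12. The protocol does not give s, so 25%, 50% and 100% are assumptions. The withdrawn fraction is w = 0.15 × s.

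**Effect on the mean UES**

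If withdrawers' mean engagement would be Δ SD below that of everyone else, and everyone else responds, the mean among those asked exceeds the mean for all enrolled by w × Δ. The values Δ = 0.5 and 1.0 are assumptions.

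| s | w | Never asked, of 396 | Never asked, of 1782 | Overstatement, Δ = 0.5 | Overstatement, Δ = 1.0 |
|---|---|---|---|---|---|
| 25% | 0.0375 | 15 | 67 | 0.02 SD | 0.04 SD |
| 50% | 0.075 | 30 | 134 | 0.04 SD | 0.08 SD |
| 100% | 0.15 | 59 | 267 | 0.08 SD | 0.15 SD |

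Using the allowance of 52 instead, the numbers never asked are 0.25 × 52 = 13 up to 52. The largest overstatement is then 0.131 × 1.0 = 0.13 SD.

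**The case against.** The strongest reply is that giving up the app is not withdrawing. Responding is optional at every prompt, so a participant who goes silent in week 3 stays enrolled and is still approached for the UES by email or telephone. A reader might infer from section 9.10 that nobody who abandons the app is ever asked, and that the 9.6.1 safeguard is therefore defeated. The documents do not support that. The safeguard reaches silent non-users and is incomplete only for formal withdrawers. One qualification applies: the investigator may discontinue a participant for "Significant non-compliance with study requirements", and then "withdrawal from the study would exclude that participant's data from the analysis if it has not already begun", so a silent non-user's place in the study is not fully secure.

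It can also be said that ending collection when someone leaves is proper. That stands. The weakness is not that the protocol honours withdrawal, but that it offers no lesser step to someone who only wants the prompts to stop.

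A reader might also infer wider losses; these are limited. The full-length PEM at 6 and 12 weeks serves criterion validity, which needs an EMCAT score on the same day (section 11.4), so it adds little once EMCAT use has ended. The Stream 2 objectives are exploratory and set appointments against a trajectory, so a record without a continuing trajectory has restricted value. It is not worthless: someone who leaves after an early open CTD appointment may already have supplied the relevant trajectory, yet 9.10 prevents the outcome being collected at the 24-week review.

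Finally, the UES is one of four usability measures. Silent disengagement will show in completion rates. Interviews, however, are also data collection, so 9.10 closes them to withdrawers too.

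**Conclusion.** The point holds for participants who formally withdraw before week 12. They are never offered the UES, and they are likely to include the most negative users. That likelihood is a judgement, supported by the protocol's own concern in 9.6.1 and its listing of app fatigue in 9.10.

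The size is small to modest: about 15 to 59 of 396 never asked, or at most 52 on the target's own allowance, and a mean UES too favourable by about 0.02 to 0.15 SD. Both ranges rest on assumed values for the share of attrition that is formal withdrawal and for how much lower withdrawers would score. The figure of 59 is an upper bound, not an estimate, because section 11.5 does not define attrition and silent non-response may be part of it.

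The effect is confined mainly to the descriptive usability objective. The primary comparison's sample size does not depend on it. This is a cheap and worthwhile improvement to the design, not an error in the main analysis.

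**What to change.** Add to section 9.10 and the consent form a level at which the participant stops the daily EMCAT prompts but remains in the study. For participants who choose it:

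- Offer the UES at that point, with their agreement, by app, email or telephone, as 9.6.1 already allows.
- Keep the 24-week record review for open CTD and steroid injection for TBOA, with their agreement.
- End all collection only on an explicit request to leave the study.

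In section 11.4, state that UES scores will be reported for completers and early stoppers separately and combined.

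The cost is an amended paragraph, a matching line in the information sheet and consent form, and a sentence on reporting. The UES contact route already exists. The small downside is that early stoppers complete the UES at varying times rather than at 12 weeks, which is a reason to show the two groups separately as well as together.

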Participants undergoing open CTD or steroid injection for TBOA will be automatically entered into a second research stream. Those undergoing steroid injection for TBOA will be followed up with twice weekly EMCAT assessments for a further 12 weeks (24 weeks total). In this stream, participants' medical records will be reviewed by members of the research team at 24 weeks. For patients with TBOA, EMCAT trajectories will be plotted as time series graphs, and follow-up appointment dates will be overlaid onto these plots. They will be inspected to see whether appointments coincide with peaks in symptom severity.

For patients undergoing open CTD, we will record whether the participant underwent any change in management as a result of their follow-up appointment (including but not limited to antibiotic prescription, reoperation, clinical investigation, arrangement of further clinical follow-up and hand therapy referral). We will then ask three independent clinicians to inspect de-identified EMCAT trajectories and predict whether or not the patient required a change in management at their follow up. We will calculate the accuracy of these predictions against what happened to the participant at their follow up.

A subsample of 10 participants recruited from the first and second research streams, and 10 clinicians, will be interviewed about their experiences of the platform. Interviews will follow a schedule that covers the following topics:

- Perceived value of the EMCAT as a data-capture platform
- Acceptability of EMCAT
- Perceived burden of EMCAT
- Facilitators and barriers to using EMCAT
- Areas for improvement within the EMCAT platform

- The potential for EMCAT's to guide follow-up in different scenarios (e.g. open CTD or steroid injections for TBOA)

Participants will be given opportunity to discuss any other aspects of the EMCAT platform they consider important.

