8.3. Exclusion Criteria

- Participant is undergoing bilateral treatments

Clinical Research Protocol Template version 15.0

- Multiple treatments to the affected hand (for any condition) are planned within the study period
- Participant is unable to engage with the EMCAT application in the English language

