11.6 Analysis populations

All participants as enrolled will be included in the analysis unless withdrawn.

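### Section 9.10 lets ineligibility that emerges after treatment remove all of a participant's data from the analysis, and a further treatment to the same hand can be read as such ineligibility

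*Protocol*

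**What the plan says.** Section 9.10 (Protocol) provides that "the Investigator may discontinue a participant from the study at any time if the Investigator considers it necessary for any reason". Among the listed grounds is "Ineligibility (either arising during the study or retrospectively having been overlooked at screening". The wording separates ineligibility missed at screening from ineligibility that develops later, and both lead to the same result: "In this case, withdrawal from the study would exclude that participant's data from the analysis if it has not already begun". The section then adds: "Where a participant has withdrawn, or been withdrawn, from the study, we will aim to replace that participant during the recruitment period".

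Participants who choose to leave are treated differently. They may allow the data gathered so far to be kept. No such option is given when the investigator withdraws someone.

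Three other sections bear on this:

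- Section 8.3 lists as an exclusion: "Multiple treatments to the affected hand (for any condition) are planned within the study period".
- Section 11.6 defines the analysis population: "All participants as enrolled will be included in the analysis unless withdrawn". Section 11.10 rules out both imputation and sensitivity analyses.
- Section 7 describes the changes in management to be recorded after open carpal tunnel decompression (CTD) as "including but not limited to antibiotic prescription, reoperation, clinical investigation, arrangement of further clinical follow-up and hand therapy referral". These are the reference-standard events for Objective 5.

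**The concern.** Eligibility criteria normally decide who enters a study, on facts known at entry. Section 9.10 also applies them afterwards and attaches exclusion of data to the result. The criterion on multiple treatments is one that a patient's clinical course can bring about: someone who recovers badly may have a further procedure planned on the same hand. If that is taken as ineligibility, the scores that recorded the poor recovery leave the analysis because of the poor recovery.

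Two analyses are affected. In the comparisons of recovery trajectories, removing poor recoveries flatters the group they came from, and by different amounts if further treatment is more common in one group. In Objective 5, a reoperated open CTD participant is a positive case that the clinicians are asked to predict. Withdrawal would take that case out of the sensitivity and predictive-value calculations. Replacing withdrawn participants restores the number but not the mix of outcomes.

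**Working it through.** **Whether the text permits it**

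1. Trigger: section 9.10 allows withdrawal for ineligibility that develops after enrolment.
2. Criterion: section 8.3 refers to multiple treatments planned for the affected hand within the study period. It does not say as of which date the plan is judged.
3. Consequence: section 9.10 excludes the participant's data, not only later scores, and section 11.6 repeats the omission.
4. Safeguards: exclusion applies only if the analysis has not begun. This protects little, because section 11.7 plans no interim analysis and section 12.5 has the app data reach the study team at the end of the study. Section 9.5 states that there is no blinding. Section 11.3 states that no separate SAP is in use.
5. Collision: section 7 names reoperation as an event for Objective 5. Antibiotics, investigations or a therapy referral would not clearly meet the section 8.3 criterion, so the overlap is with reoperation or another treatment to the same hand.

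**The plan's own figure**

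Section 11.5 gives an effect of 0.35, SD 1, 5% significance (taken as two-sided) and 90% power. The standard formula for two means gives 172 per group and 344 in total, as stated.

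**Primary comparison (assumed inputs)**

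Let a fraction f of one arm score m SD worse than the rest of that arm. The full-arm mean is then f × m worse than the mean of the rest, so removing these people shifts the arm mean by f × m. Replacements who are not themselves removed score like the rest, so the shift remains.

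| f | m | Shift (SD) | Share of 0.35 | Power at 172 per group if the difference shrinks by the shift |
|---|---|---|---|---|
| 2% | 0.5 | 0.02 × 0.5 = 0.01 | 3% | 88% |
| 2% | 1 | 0.02 × 1 = 0.02 | 6% | 86% |
| 5% | 0.5 | 0.05 × 0.5 = 0.025 | 7% | 85% |
| 5% | 1 | 0.05 × 1 = 0.05 | 14% | 79% |

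The power column assumes removal only from the arm expected to score worse, which narrows the difference. Removal from the other arm would widen it, and equal removal from both would largely cancel.

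**Objective 5 (assumed inputs)**

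Take 198 open CTD participants, which is the maximum and not a target, with 10-20% having a change in management: 198 × 0.10 ≈ 20 to 198 × 0.20 ≈ 40 positives. If 2-5% were removed for reoperation, 198 × 0.02 ≈ 4 to 198 × 0.05 ≈ 10 would be lost.

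- Low with low: 4/20 = 20%.
- High with high: 10/40 = 25%.
- Opposite extremes: 4/40 = 10% and 10/20 = 50%.

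Sensitivity would move too. Suppose clinicians detect 90% of reoperations and 50% of other changes. If reoperations are 10% of positives, true sensitivity is 0.10 × 0.9 + 0.90 × 0.5 = 0.54. If they are 50%, it is 0.50 × 0.9 + 0.50 × 0.5 = 0.70. With every reoperation removed, 0.50 would be reported in both cases.

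**The case against.** The link from section 8.3 to a later reoperation is an inference. Section 9.2 places the check of exclusion criteria at recruitment, and section 9.12 puts recruitment on the day of treatment, before it. The natural reading is therefore treatments already planned at that point. Ineligibility that develops later also has ordinary uses: a participant may not go on to have the eligible treatment, or may become unable to use the app. Sections 7, 9.12 and 12.5 set up a record review that captures changes in management, which suggests that reoperation is meant to be kept as an outcome.

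The route is also weak for the primary comparison. Section 9.8 has no later visits, and the record review covers only open CTD and steroid injection for thumb-base osteoarthritis. No planned data collection would show a reoperation after limited fasciectomy or needle fasciotomy. Withdrawal is discretionary, its reason is recorded in the study file, and Objective 5 is exploratory.

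Most of this stands, and it limits how far the point goes:

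- A reader might infer that records are deleted. Section 9.10 says only that data are left out of the analysis.
- A reader might infer that reoperation always makes a participant ineligible, so that the protocol contradicts itself. No section says so; it is one available reading.
- A reader might infer that the primary trajectories will look better than they were. The documents do not show that such withdrawals would occur, or in which arm.
- A reader might infer that half of the Objective 5 positives could be lost. That pairs the highest assumed number removed with the lowest assumed number of positives, and section 7's definition also covers several milder events.

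What the objection does not remove is the wording. Section 9.10 expressly covers ineligibility that develops after enrolment, nothing limits that to harmless cases, and discretion lets sites apply it differently.

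**Conclusion.** The point holds as a defect in a stated rule, not as a demonstrated bias. Section 9.10 permits scores already collected to be excluded for a reason that can depend on how the patient recovered, section 11.6 carries the exclusion into the analysis, and with no sensitivity analyses planned its effect would not be examined.

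The size cannot be derived from the documents, which give no rate of further treatment or of changes in management. For the primary comparison it is probably small: 0.01-0.05 SD, or 3-14% of the design effect, if 2-5% of one arm scoring 0.5-1 SD worse is removed. Objective 5 is more sensitive because positives may be few and reoperation is among the more serious of them. Its figures assume that every reoperated participant is withdrawn, which the discretionary wording does not require.

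**What to change.** In section 9.10:

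- Limit exclusion of data for ineligibility to criteria that were already unmet at enrolment, judged on facts from before the treatment.
- State that a further treatment decided after the study treatment is not ineligibility.
- Keep these participants' collected scores in the analysis, at minimum all scores up to the further treatment. Cutting off at that date is itself triggered by clinical course, so settle in advance whether later scores are used and apply the choice alike in both groups.
- For open CTD, count the event as a change in management in Objective 5.

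Reword section 11.6 so that its exception for withdrawn participants matches. A clause in section 8.3 that the planned treatments are those known at enrolment would remove the remaining ambiguity.

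The cost is a few sentences. No extra patients or visits are needed, slightly fewer participants would be replaced, and clinical care is untouched. The change should be made before analysis, since exclusion that depends on outcome cannot be reliably repaired afterwards.
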